The EQ-5D-5L is a standardized measure of health status developed by the EuroQol Group in order to provide a simple, generic measure of health for clinical and economic appraisal (*Herdman et al. 2011*). The EQ-5D-5L (Appendix 5) includes five levels of severity in each of the five EuroQol-5D dimensions and the EQ VAS. The descriptive system comprises 5 dimensions (mobility, self-care, usual activities, pain/discomfort, anxiety/depression), each dimension having 5 levels (no problems, slight problems, moderate problems, severe problems, and extreme problems). The EQ VAS records the respondent's self-rated health on a vertical, visual analogue scale numbered from 0 to 100 with endpoints labelled 'the best health you can imagine' and 'the worst health you can imagine'.

The EQ-5D-5L will be completed at baseline, every three months and at the end of the study, as well as at each episode of bleeding.

VAS for pain (via ePRO)

The intensity of pain in the main joints (elbow, knee, ankle) will be evaluated (at baseline, every month and at the end of the study, as well as at each bleeding episode) by means of a 100 mm VAS and will be recorded through ePRO application.

The VAS is an instrument that measures the amount of pain that a patient feels across a continuum from none to an extreme amount of pain.

Operationally a VAS is usually a horizontal line (see example below), 100 mm in length, anchored by word descriptors at each end, where the left extreme means "No pain = 0" while the right extreme means "Worst Pain Imaginable = 100".

After sitting for 15 minutes, the extent of pain at the injury site will be evaluated in answer to the question: "How would you describe your injury related pain right now?"

Patients will mark on the line the point that they feel representing their perceived pain. The VAS score is the distance (in millimeters) from the left end of the line to the point where the patient's mark crossed the line.

It has been demonstrated that the measurement of the response VAS scale collected on paper and by electronic administration, using BYOD or a site-provisioned device, are equivalent. In addition, there is no evidence of a difference in measurement properties of each response scale type across different screen sizes of devices (*Bill Byrom et al. 2018*)

Caregiver burden

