- Body Mass Index (BMI) evaluated at baseline and every three months.
- Number of days away from school (patient) and/or work (patient and caregiver), and age of possible early retirement (caregiver) during the observation period, evaluated through administration of questions (evaluated at baseline, every month, and at the end of the study).
- Number of hospitalization days (patient) during the observation period evaluated through administration of questions (evaluated at baseline, every month, at the end of the study).
- Pain intensity measured using a Visual Analogue Scale (VAS) (evaluated at baseline, every month and at the end of the study).

The intensity of pain will be evaluated at baseline, every month and at the end of the study, as well as at each bleeding episode, by means of a 100 mm VAS and will be recorded through ePRO application. The left extreme of the horizontal line means “No pain = 0” while the right extreme means “Worst Pain Imaginable = 100”.

- To evaluate adherence to the treatment regimen: documented during planned visits according to source data (ePRO data) in electronic Case Report Forms (eCRF) by the investigator.

The adherence to the treatment regimen will be analyzed as proportion of “Yes” and “My therapeutic plan does not include any treatment in the last week” on the total of week reported via the ePRO. Missing data for some weeks will be treated as “No”. The total number of weeks will be derived as:

$$(End\ of\ study\ date - Baseline\ date + 1) / 7$$

- To describe the active vs. sedentary haemophiliac patients in terms of:
  - Severity of disease
  - Annualized bleeding rate (ABR)

The annualized bleeding rate will be derived as follows:

$$\frac{\text{total number of bleeds}}{\text{sum of the individual study's durations}}$$

where the individual study's duration will be given by

$$\text{end of study date} - \text{baseline date} + 1$$

- Pain and use of painkillers (as described above).
- Drug regimen adopted (as described above).
- HRQoL (as described above).
- Hospitalization/missed days at school (as described above).
- Joint Health Status (as described above).
- To describe severe vs moderate haemophiliac patients for the above mentioned items.

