#### **4.4.2 Secondary and Exploratory Endpoints**

The endpoints assessed via the ePRO application that require to be evaluated at specific timepoint need to be “remapped” at each time point by deriving from the date the corresponding week/month starting from the baseline date. In case that more than one observation occurs within the same week/month, the mean among the two observations will be used.

**To document physical activity, particularly in terms of active minutes, by ages categories (12-17, 18-30 and 31-50 years), by type of physical activity and by intensity (as per fitness tracker default categorization)**

Data will be analyzed as for the primary endpoint described in Section 4.4.1 but they will be analyzed at activity level (instead of a daily level).

For example, if we consider “Bike”, the active minutes and METs will be derived as median of the active minutes (heart zone minutes, active zone minutes and MVPA minutes) for single activity (i.e. if Bike is reported twice, the active minutes for Bike will be derived as median of the values reported for each of two activities done).

Moreover, the activity rate will be derived as follow (in the example for “Bike”):

$$\text{Bike weekly rate} = \frac{\text{number of times that Bike is reported on the fitness tracker}}{\text{end of study date} - \text{baseline date} + 1} \times 7$$

For each type of activity, the statistics will be shown overall and by age groups (12-17, 18-30 and 31-50). The comparison among the age groups will be performed by means of a one-way ANOVA or, if assumptions of normality is not confirmed (by a visual inspection: histogram and qq-plot), by means of a Kruskal-Wallis test.

Daily physical activity will also be summarized:

- by start of any newly approved drug for haemophilia (see Section 4.4.4 for subgroup definition).
- by COVID-19 period on the EVL population (see Section 4.4.4 for subgroup definition).
- by month through the entire observational period on the EVL to observe the impact of COVID-19.

Data will be summarized at activity level considering data collected in each period above-mentioned.

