#### **Health-Related Quality of Life (HRQoL) and health status reported during routine clinical practice, measured using the European Quality of Life-5 Dimensions (EQ-5D-5L) score**

The EQ-5D-5L score will be analyzed at baseline and monthly up to the end of the observational period. The month will be derived as: rounded[(reference date – baseline date + 1) /30.4375].

The EQ-5D Index Utility Score as well as the EQ VAS Score will be analyzed according to their continuous nature. The change from baseline will also be shown. The 95%CIs for the mean and for the mean change from the baseline will also be calculated.

Moreover, the score related to each dimension (mobility, selfcare, usual activity, pain/discomfort and anxiety/depression) will be analyzed according to its categorical nature in the overall sample. Number and proportion of patients in each category will be displayed (No problems, Slight problems, Moderate problems, Severe problems, Extreme problems).

Data will also be summarized:

- by start of any newly approved drug for haemophilia (see Section 4.4.4 for subgroup definition).
- by COVID-19 period (see Section 4.4.4 for subgroup definition).
- by month through the entire observational period to observe the impact of COVID-19.

In case of more than 1 value for each subject in each period, the continuous variable will be replaced by using the mean of the value for each subjects, the qualitative variables (e.g. the score domain) will be replaced by the worst value.

Other subgroup analyzes: frequency of physical activity, severity of the disease (see Section 4.4.4 for subgroup definition).

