**Age of possible early retirement (caregiver)**

The age of possible early retirement of the parent/caregiver will be analyzed at the end of the study as described in section 4 for continuous variables.

Other subgroup analyzes: severity of the disease, start of any newly approved drug for haemophilia (see Section 4.4.4 for subgroup definition).

**Number of hospitalization days (patients) during the observation period evaluated through administration of questions (evaluated at baseline, every month, at the end of the study)**

The number of hospitalization days (related to haemophilia and collected via ePRO) will be analyzed at baseline, every month and at the end of the study as a continuous variable as well as number and proportion of patients who were hospitalized during the previous month.

An overall measure of the hospitalization days for one year will be derived for each patient as proportion between the total number of hospitalization days and the period defined as (end of study date – baseline date + 1) multiplied by 365.25. This parameter will be analyzed as a continuous variable and shown along with the 95%CI.

Other subgroup analyzes: frequency of physical activity, severity of the disease, start of any newly approved drug for haemophilia (see Section 4.4.4 for subgroup definition).

**Pain intensity measured using a Visual Analogue Scale (VAS) (evaluated at baseline, every month, and at the end of the study)**

The pain intensity will be analyzed at baseline and monthly up to the end of the observational period. The month will be derived as: rounded[(reference date – baseline date + 1) /30.4375].

The VAS for pain score will be analyzed as value at each timepoint and as change from baseline.

The 95%CIs for the mean and for the mean change will be also displayed.

Pain intensity will also be summarized:

- by start of any newly approved drug for haemophilia (see Section 4.4.4 for subgroup definition).
- by COVID-19 period (see Section 4.4.4 for subgroup definition).
- by month through the entire observational period to observe the impact of COVID-19.

Other subgroup analyzes: frequency of physical activity, severity of the disease (see Section 4.4.4 for subgroup definition).

**To evaluate adherence to the treatment regimen: documented during planned visits according to source data (ePRO data) in electronic Case Report Forms (eCRF) by the investigator.**

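### The month formula for EQ-5D-5L and pain VAS gives month 0 to the first 14 days after baseline, so a bleed-triggered entry there can be averaged into an undefined baseline

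*SAP*

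**What the plan says.** SAP 4.4.2 analyses EQ-5D-5L at baseline and then monthly. The rule begins "The month will be derived as: rounded", and the expression in full is "rounded[(reference date – baseline date + 1) /30.4375", bracket closed. The same formula is printed for pain: "The pain intensity will be analyzed at baseline and monthly up to the end of the observational period". Change from baseline, with a 95% CI for the mean change, is planned for the EQ-5D index, EQ VAS and pain VAS.

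The opening of SAP 4.4.2 says how ePRO entries reach a timepoint: "by deriving from the date the corresponding week/month starting from the baseline date". It continues: "In case that more than one observation occurs within the same week/month, the mean among the two observations will be used". For several EQ-5D values in one period, the HRQoL text also uses the mean for continuous scores, but for categories "the qualitative variables (e.g. the score domain) will be replaced by the worst value".

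Both instruments have a bleed trigger. For EQ-5D-5L, Protocol 6.4.1 (HRQoL) plans completion at baseline, "every three months and at the end of the study, as well as at each episode of bleeding". For pain, SAP 2.2.1 adds to the monthly schedule "as well as at each bleeding episode, by means of a 100 mm VAS", and Protocol 6.4.1 agrees. The EQ-5D trigger is not stated consistently. SAP 2.2.1 and footnote 9 of both schedule tables list only baseline, every three months and end of study, while footnote 7 mentions health status information at a bleed.

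The schedule tables (Protocol Appendix 2, SAP Appendix 2) place the baseline visit at time 0. SAP 4.4.4 defines an ePRO baseline only for the period after a switch to a newly approved drug.

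**The concern.** A baseline should describe the patient before follow-up starts. Here the date alone assigns the timepoint, the month-0 window runs two weeks past baseline, and entries inside a window are pooled whatever prompted them. Pain and health status can reasonably be expected to be worse during a bleed than at a routine visit. A bleed in the first fortnight would then make the reference value too poor, and that one error would carry into every later change for the patient.

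The change-from-baseline summaries for three secondary scores are at stake. Both endpoints are also described by disease severity. If bleeding rates differ between severe and moderate patients, the two groups would be affected unequally.

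**Working it through.** The SAP states no width for the month-0 window, so there is no planned figure to reproduce. The check evaluates the printed formula.

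**Windows.** Let d = entry date minus baseline date, and month = round((d + 1)/30.4375).

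| d | (d + 1)/30.4375 | month |
|---|---|---|
| 0 | 1/30.4375 = 0.033 | 0 |
| 14 | 15/30.4375 = 0.493 | 0 |
| 15 | 16/30.4375 = 0.526 | 1 |
| 44 | 45/30.4375 = 1.478 | 1 |
| 45 | 46/30.4375 = 1.511 | 2 |

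After baseline, month 0 is therefore days 0 to 14 and month 1 is days 15 to 44. Later windows are 30 or 31 days long.

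**Exclusions.** The only date limit on ePRO data (SAP section 4) runs from consent to completion or withdrawal. Nothing removes post-baseline or bleed-triggered entries from month 0.

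**One patient (assumed values).** The scheduled baseline pain is 20, and a bleed entry on day 10 is 60.
- Month-0 mean: (20 + 60)/2 = 40.
- A later scheduled entry of 20 shows a change of 20 - 40 = -20. The true change is 0.
- If that later month also holds a bleed entry of 60, its mean is 40 and the change is 40 - 40 = 0. With a clean baseline but a mixed later month, the change would be 40 - 20 = +20.

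**Share affected at baseline.** The documents give no bleeding rate, so r bleeds per year is an assumption. P(at least one bleed in 14 days) = 1 - exp(-14r/365.25).
- r = 2: 1 - exp(-0.0767) = 7.4%, about 8 of the 107 enrolled.
- r = 5: 1 - exp(-0.1917) = 17.4%, about 19 of 107.

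**Later months.** For a 30-day window, P = 1 - exp(-30r/365.25).
- r = 2: 15.1%.
- r = 5: 33.7%.

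**Cohort mean, pain VAS.** Assume one scheduled entry per window and a bleed entry 40 mm worse, so an affected window moves by 20 mm.

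| r | Shift in month 0 | Shift in a later month | Net shift in mean change |
|---|---|---|---|
| 2 | 0.074 x 20 = 1.5 | 0.151 x 20 = 3.0 | about +1.6 |
| 5 | 0.174 x 20 = 3.5 | 0.337 x 20 = 6.7 | about +3.2 |

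Net shifts are taken before rounding. A positive value means apparent worsening.

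**The case against.** The strongest reply is that the SAP never equates month 0 with baseline. SAP 4.4.2 names baseline and the monthly timepoints separately, the averaging rule mentions only week and month, and the post-switch baseline in SAP 4.4.4 is visit-based. A programmer could hold the baseline-visit entry apart, and the mock shells, which are a separate attachment, might show this. That stands as a limit: the averaging follows from the stated rules plus the time-0 schedule, not from an explicit sentence. It does not remove the problem, because entries on days 1 to 14 would then belong to no reported timepoint. Either reading needs a rule.

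A reader might also infer that later changes will look too favourable across the cohort. The documents do not support that. Later windows are about twice as long and absorb bleed entries under the same rule. In the illustration above, the net shift for pain goes towards worsening.

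Three further limits stand. The formula is printed only for EQ-5D-5L and pain VAS, so the point does not extend to all ePRO data. The EQ-5D bleed trigger is stated in Protocol 6.4.1 but missing from SAP 2.2.1 and footnote 9. Finally, these are descriptive secondary results in an exploratory study, with full data listings and a data review meeting before lock.

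**Conclusion.** The point holds for EQ-5D-5L and pain VAS. The printed formula assigns days 0 to 14 to month 0, and this is exact. With baseline at time 0, date-only remapping, same-month averaging and no definition of the study baseline, the rules as written mix early bleed-triggered entries into the change reference. For the EQ-5D dimensions, if the worst-value rule is applied to month 0, an early bleed entry could replace the baseline category outright.

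About 7% of patients would have a bleed in that fortnight at 2 bleeds per year and 17% at 5, assuming Poisson bleeding at rates that the documents do not give. The 20 mm shift for an affected patient is likewise illustrative.

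Changes from baseline are distorted at both ends, because bleed-triggered and scheduled entries are also pooled in later months. Neither the size nor the sign of the net effect on the cohort mean can be established from the documents. This is a minor point, but it should be settled before the derivations are final.

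**What to change.** In SAP 4.4.2:

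1. Define the ePRO baseline as the scheduled baseline questionnaire: the first entry not triggered by a bleed, made at the baseline visit or within a short, stated window after it. Never average it with later entries. Accepting only entries dated on or before baseline would be riskier. Patients are trained on the app at the baseline visit and SAP 4.7 imputes nothing, so a patient whose first entry came late would drop out of every change analysis.
2. Start the month 1 window immediately after the baseline window.
3. At all timepoints, use scheduled entries for the monthly values and changes from baseline, and summarise bleed-triggered entries separately. Cleaning baseline alone would leave bleed entries in the later months.
4. Reconcile the EQ-5D bleed trigger in Protocol 6.4.1 with SAP 2.2.1 and schedule footnote 9.

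The cost is SAP wording and one derivation rule, applied to entries that are already dated and bleeds that are already recorded. The downside is fewer EQ-5D values in months with no scheduled questionnaire, since the schedule is quarterly.

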### **Dose and frequency of concomitant medications taken to control pain**

Only concomitant medication for pain treatment will be displayed. Frequency distributions and percentages will be summarized in the Evaluable population by Anatomical Main Group (1st level of the Anatomical Therapeutic Chemical (ATC) classification), Chemical Subgroup (4th level of the ATC classification) and Preferred Name.

Subjects taking more than one medication classified in the same anatomical main group, chemical subgroup and preferred name will be counted only once.

Other subgroup analyzes: frequency of physical activity, severity of the disease, start of any newly approved drug for haemophilia (see Section 4.4.4 for subgroup definition).

### **Joint health status of enrolled patients, based on Haemophilia Joint Health Score (HJHS) questionnaire (evaluated at baseline, at six months, and at the end of the study)**

The HJHS will be analyzed according to its continuous nature. The statistics will be displayed at each timepoint (baseline, 6 months and 12 months) for the HJHS Total Score and for the Global Gait Score along with the 95%CIs for the mean. The change from the baseline values will also be analyzed.

The score related to each joint (elbow, knee and ankle, left and right side respectively) will be listed.

Other subgroup analyzes: frequency of physical activity, severity of the disease, start of any newly approved drug for haemophilia (see Section 4.4.4 for subgroup definition).

### **Body Mass Index (BMI) evaluated at baseline and every three months**

The BMI will be analyzed at each timepoint (baseline, every 3 months and at end of study) by means of the descriptive statistics for continuous variables. The change from the baseline value will be also derived and analyzed at each timepoint after the baseline.

The statistics will be displayed for the value and for the change from baseline along with the 95%CIs for the mean.

Other subgroup analyzes: severity of the disease, start of any newly approved drug for haemophilia (see Section 4.4.4 for subgroup definition).

**Number of days away from school (patient) and/or work (patient and caregiver), and age of possible early retirement (caregiver) during the observation period, evaluated through administration of questions (evaluated at baseline, every month, and at the end of the study)**

**Patients**

The number of days away from school or work (patient) will be analyzed every month as a continuous variable as well as number and proportion of patients who missed at least one day of school or work.

An overall measure of the days away from school and/or work in one year will be derived for each patient as proportion between the total number of days away from school and/or work and duration of the study (derived as end of study date – baseline date + 1) multiplied by 365.25. This parameter will be analyzed as a continuous variable and shown along with the 95%CI.

Other subgroup analyzes: severity of the disease, start of any newly approved drug for haemophilia (see Section 4.4.4 for subgroup definition).

**Caregiver**

The number of days away from work will be analyzed every month as a continuous variable as well as number and proportion of patients who missed at least one day of work.

An overall measure of the days away from work of the parent/caregiver in one year will be derived for each patient as proportion between the total number of days away from work and duration of the study (derived as end of study date – baseline date + 1) multiplied by 365.25. This parameter will be analyzed as a continuous variable and shown along with the 95%CI.

Other subgroup analyzes: severity of the disease, start of any newly approved drug for haemophilia (see Section 4.4.4 for subgroup definition).

**Age of possible early retirement (caregiver)**

The age of possible early retirement of the parent/caregiver will be analyzed at the end of the study as described in section 4 for continuous variables.

Other subgroup analyzes: severity of the disease, start of any newly approved drug for haemophilia (see Section 4.4.4 for subgroup definition).

**Number of hospitalization days (patients) during the observation period evaluated through administration of questions (evaluated at baseline, every month, at the end of the study)**

The number of hospitalization days (related to haemophilia and collected via ePRO) will be analyzed at baseline, every month and at the end of the study as a continuous variable as well as number and proportion of patients who were hospitalized during the previous month.

An overall measure of the hospitalization days for one year will be derived for each patient as proportion between the total number of hospitalization days and the period defined as (end of study date – baseline date + 1) multiplied by 365.25. This parameter will be analyzed as a continuous variable and shown along with the 95%CI.

Other subgroup analyzes: frequency of physical activity, severity of the disease, start of any newly approved drug for haemophilia (see Section 4.4.4 for subgroup definition).

**Pain intensity measured using a Visual Analogue Scale (VAS) (evaluated at baseline, every month, and at the end of the study)**

The pain intensity will be analyzed at baseline and monthly up to the end of the observational period. The month will be derived as: rounded[(reference date – baseline date + 1) /30.4375].

The VAS for pain score will be analyzed as value at each timepoint and as change from baseline.

The 95%CIs for the mean and for the mean change will be also displayed.

Pain intensity will also be summarized:

- by start of any newly approved drug for haemophilia (see Section 4.4.4 for subgroup definition).
- by COVID-19 period (see Section 4.4.4 for subgroup definition).
- by month through the entire observational period to observe the impact of COVID-19.

Other subgroup analyzes: frequency of physical activity, severity of the disease (see Section 4.4.4 for subgroup definition).

**To evaluate adherence to the treatment regimen: documented during planned visits according to source data (ePRO data) in electronic Case Report Forms (eCRF) by the investigator.**

The adherence will be summarized as a continuous variable as described in the introduction of Section 4. Moreover, the number and proportion of subjects who have a compliance of at least 80% will be shown.

The adherence to the treatment regimen will be analyzed as proportion of “Yes” and “My therapeutic plan does not include any treatment in the last week” on the total of week reported via the ePRO. Missing data for some weeks will be treated as “No”. The total number of weeks will be derived as the ceil of (End of study date – Baseline date + 1) / 7.

The main reasons for no assumption, change of the dose or frequency will be listed.

Adherence to treatment regimen will also be summarized:

- by start of any newly approved drug for haemophilia (see Section 4.4.4 for subgroup definition).
- by COVID-19 period (see Section 4.4.4 for subgroup definition).
- by month through the entire observational period to observe the impact of COVID-19.

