4.1 STUDY RATIONALE

There are few data on physical activity in patients with Haemophilia. Previous studies have generally included small samples of patients and none has been conducted in Italy.

The rationale for conducting this non-interventional study (NIS) is to collect information about activity status, bleeds, health-related quality of life (HRQoL) and health status in patients with moderate or severe haemophilia A without inhibitors, who are being treated in accordance with normal clinical practice.

This NIS aims to provide robust documentation about activity levels, bleeds, HRQoL and health status (in adults/adolescents) in patients with Haemophilia A treated according to local routine clinical practice (receiving FVIII replacement therapy or bypassing agents as either episodic or prophylactic treatment).

Furthermore, new upcoming therapies for haemophilia A will likely continue to change clinical practice. Ranging from new extended half-life replacement therapies, to nonfactor products and gene therapy, these innovative approaches have the potential to enhance the standard of care by decreasing infusion frequency, easing route of administration, in some cases also ensuring more efficacy, reducing the risk of bleeds, and in particular the number of target joint bleeds, all characteristics that could have a significant impact on physical activities and quality of life.

Therefore, in this study it has been considered of interest to collect information on physical activity status bleeds, HRQoL and health status in patients that will start treatment with any new drug, if approved during the course of the study for the treatment of Haemophilia A without factor VIII inhibitors, *i.e.* the population object of the study.

In case of start of treatment with any newly approved treatments during the study, the patient will be observed, on primary and secondary objectives, for a minimum period of 6 months.

The data from this study may be used to compare with data from ongoing interventional studies or to refine assumptions pertaining to patient characteristics, to enhance the design of new interventional or non-interventional studies.

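### Weeks with no planned treatment count as adherent, so the score measures diary completion in on-demand patients and mixes regimen with behaviour around a switch

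*SAP*

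**What the plan says.** SAP 2.2.1 introduces the measure: "The adherence to the treatment regimen will be analyzed as proportion of" weeks answered 'Yes' plus weeks answered "My therapeutic plan does not include any treatment in the last week". SAP 4.4.2 (adherence to the treatment regimen) repeats this and adds three rules:

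- **Missing weeks.** "Missing data for some weeks will be treated as" 'No'.
- **Denominator.** It is given first as "on the total of week reported via the ePRO", then as a calendar count: "The total number of weeks will be derived as the ceil of" (end of study date – baseline date + 1)/7. SAP 2.2.1 gives the calendar count without rounding up ("The total number of weeks will be derived as" the plain quotient).
- **Reporting.** Adherence is summarised as a continuous variable, and the "number and proportion of subjects who have a compliance of at least 80% will be shown".

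The SAP 4.4.2 paragraph also asks for adherence by start of a newly approved drug. SAP 4.4.4 defines that as before and after the switch, and by replacement or non-replacement therapy. Nothing restricts or splits adherence by regimen. Protocol 4.1 admits patients on episodic as well as prophylactic treatment. SAP 4.1.3 applies the objectives to the Evaluable and ITT populations (ITT alone for this endpoint if the Evaluable set is under half of those enrolled).

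On new therapies, Protocol 4.1 says that they "have the potential to enhance the standard of care by decreasing infusion frequency". It gives no dosing interval.

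**The concern.** In a week with nothing scheduled there is no treatment to take or miss, so adherence is not observed. The SAP nevertheless credits such a week in full. Two results become hard to interpret.

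First, for a patient whose plan contains no scheduled treatment, every answered week scores as adherent. That patient's percentage, and whether the 80% mark is passed, carries no information about taking treatment, yet it is averaged with prophylaxis patients.

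Second, the share of no-plan weeks depends on the regimen, and a switch changes the regimen. A before/after difference can therefore arise with no change in what the patient does when a dose is due. Protocol 6.1.2 sets out to document the effect of new therapies against the previous standard of care, and names better compliance through fewer infusions as one expected route. A measure that moves with the schedule alone cannot separate the two.

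**Working it through.** The documents state no adherence figure, so there is none to reproduce. The check applies the SAP rule directly.

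**Inputs from the SAP.** Numerator = 'Yes' weeks + no-plan weeks; missing week = 'No'; denominator = ceil(days/7); threshold 80%.

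**Assumptions (not in the documents).** *r* = share of weeks answered, the same in planned and no-plan weeks. *p* = chance of 'Yes' in an answered week with planned treatment. One planned dose every *k* weeks, with *k* = 1, 2, 4 for illustration only.

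**Step 1. Patient with no planned weeks, always answering no-plan, followed for 365 days.** The denominator is ceil(365/7) = ceil(52.14) = 53.

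- 53/53 = 100%; 52/53 = 98.1%; 48/53 = 90.6%
- 43/53 = 81.1% (passes 80%)
- 42/53 = 79.2% (fails 80%)
- 37/53 = 69.8%

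The score is diary completion. If only the 52 full weeks can be reported, the maximum is 98.1%. With weeks reported as the denominator, any number *n* of answered weeks gives *n*/*n* = 100%. With the unrounded total in SAP 2.2.1, 42 answered weeks give 42/52.14 = 80.5% and pass. The three denominators therefore classify the same patient differently.

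**Step 2. Patient on a schedule.** A share (k−1)/k of weeks has no planned dose, so

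score = r × [(k−1)/k + p/k].

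| k | r = 1, p = 0.8 | r = 1, p = 0.6 | r = 0.8, p = 0.8 |
|---|---|---|---|
| 1 | 80% | 60% | 64% |
| 2 | 90% | 80% | 72% |
| 4 | 95% | 90% | 76% |

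Within each column, behaviour in planned weeks is identical. At r = 1 and p = 0.6, moving from k = 1 to k = 2 takes the patient from 60% to the 80% threshold.

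**Step 3. Limits on the direction.**

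- If treatment is planned every week before and after the switch, k = 1 in both periods and the rule adds nothing.
- At p = 0.8, a fall in completion to 0.80/0.90 = 88.9% of its earlier level (k = 2), or 0.80/0.95 = 84.2% (k = 4), cancels the rise.
- An on-demand patient who starts weekly prophylaxis goes from r to r × p: 100% to 80% at r = 1, p = 0.8.

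**Step 4. Two candidate corrections at r = 0.8, p = 0.8.**

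- *Remove only the reported no-plan weeks and keep every missing week as 'No'.* Score = (r·p/k) / [1 − r(k−1)/k]. For k = 1: 0.64/1 = 64%. For k = 2: 0.32/0.60 = 53%. For k = 4: 0.16/0.40 = 40%. The distortion now runs the other way, and an on-demand patient with one missing week scores 0/1 = 0%.
- *Count planned weeks only, and score only planned missing weeks as 'No'.* Score = r × p = 64% for every k. A patient with no planned weeks gives 0/0, that is, not applicable.

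**The case against.** The strongest defence is that a week in which the plan asked for nothing, and nothing was taken, did follow the regimen. On that definition, crediting it is coherent. The endpoint is also one descriptive secondary measure in an exploratory non-interventional study, with no test planned on it. Regimen is tabulated and listed separately in SAP 4.4.2. Neither the ePRO question nor the mock shells are available here.

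This limits the importance but does not rescue the two uses in question. Even on that definition, the 80% threshold in an on-demand patient reflects only whether the diary was answered, and the before/after contrast still moves with the schedule.

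Two stronger readings are tempting, and the documents do not support them. A reader might infer that on-demand patients score 100% automatically. The missing-as-'No' rule over calendar weeks prevents that; it follows only from the competing weeks-reported denominator. A reader might also infer that the switch comparison is structurally biased towards the new drug. That needs whole weeks without planned treatment and stable completion. The documents give no intervals and speak only of potential, and Protocol 5.2.2 limits newly approved drugs to prophylaxis, so an on-demand switcher moves the other way. The net direction depends on the mix of switchers, which is not given.

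**Conclusion.** The point holds in a limited form. As written, the score measures diary completion, or a constant 100% under the other denominator, in any patient with no planned weeks. Around a switch it mixes regimen with behaviour, in a direction that cannot be fixed in advance.

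The illustrative size is 10 to 15 percentage points at p = 0.8 with full completion (80% to 90% or 95%), zero if treatment is planned every week, and minus 20 points for an on-demand patient starting weekly prophylaxis. These sizes rest on the assumed r, p and k. The effect on the overall mean cannot be stated, because the number of on-demand patients is not given and scoring missing weeks as 'No' pulls the other way. The endpoint is secondary, but its pooled and before/after-switch figures cannot be read as adherence, and the change should be made.

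**What to change.** Amend SAP 2.2.1 and 4.4.2 as follows:

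1. Base the main adherence summary and the 80% threshold on weeks with planned treatment, in patients on prophylaxis. Report on-demand patients separately as not applicable.
2. Classify each unreported week as planned or not planned from the regimen already recorded (therapy, dose and frequency), and score only planned missing weeks as 'No'. Removing the reported no-plan weeks alone is not enough.
3. Show planned weeks and diary completion per patient beside the score.
4. Compute the denominator within each pre- and post-switch period, since the present formula runs from baseline to end of study.
5. Keep one denominator: reconcile weeks reported with the calendar total, and align the two sections on rounding up.
6. State whether no-plan weeks count as adherent in the measure for the week before a bleed (SAP 4.4.2, treatment regimen for bleeding).

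The cost is SAP wording and some derivation work for missing weeks, including a rule for weeks in which the regimen changes. No new data are collected. Patients with no planned weeks will have no adherence value, so the number contributing will be smaller and should be shown.
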